7.7 Sensitivity analyses of primary endpoints

Sensitivity analyses will be performed on the FAS#2.

(1) Missing data

To account for the effect of both missing data (e.g. missing FST-YSI^{TM*}, existing FST-YSI^{TM*} value without paired SG point, etc.), and FST-YSI^{TM*} with deletion flag (from protocol deviations collected by CRF) for primary endpoints evaluation, relevant sensitivity analyses for primary endpoints will also be provided.

In these analyses, the missing paired YSI-SG will be handled based on worst case, best case and randomly pick from the same subject methods, respectively. (See section 6.5). The 20/20% agreement rate, a mean rate in Zone A+B of Clarke and Consensus Error Grid based on measurement level will be analyzed after missing data being handled according to above different methods in sensitivity analysis.

(2) Site Effect

Investigative site effect will be evaluated using the generalized estimation equation (GEE) for 20/20% agreement rate, a mean rate in Zone A+B of Clarke and Consensus Error Grid and the linear regression

model for MARD. If site effect is detected, sensitivity analysis will be performed using the random-effects models to obtain combined effect for endpoints. If the random-effects model is not feasible then the estimation of fixed-effects model will be provided. Inverse variance method (weight=1/variance of site estimate) will be used in the analysis.

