6.3 Analysis Population

Full analysis set (FAS#1): a set of subjects who have at least one Guardian Sensor inserted.

Full analysis set (FAS^{#2}): a set of subjects who have at least one Guardian Sensor inserted and have at least one paired Guardian Sensor and YSI^{TM*} measurement.

Per-Protocol Set (PPS) refer to the subgroup population of FAS^{#2} who have no major protocol deviations (subjects that violate the inclusion criteria, meet the exclusion criteria, etc.).

Safety Set (SS) refer to all enrolled subjects.

Primary efficacy analysis will be analyzed based on both the FAS^{#2} and PPS. All the baseline demographic data will be analyzed based on the FAS^{#1}. Safety evaluation will be analyzed based on SS.

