6.4 Analysis Population Set Determination Details

- (1) No Guardian Sensor inserted: Subjects obtain randomly assigned FST, but have no Guardian Sensor inserted.
- (2) No paired Guardian Sensor and YSI TM* measurement: Subjects obtain randomly assigned FST and have a Guardian Sensor inserted, but have no paired Guardian Sensor and YSI measurement.
- (3) Violation of Inclusion/Exclusion criteria: Subjects do not meet the inclusion criteria or meet the exclusion criteria pre-specified in the protocol, and this protocol deviation may severely affect the results of primary effective endpoint. Whether protocol deviation severely affect the results of primary effective endpoints will be judged together by sponsor, investigators and statistician through discussion;
 - (4) SS= Number of subjects enrolled;

FAS#1= Number of the subjects randomly assigned FST- Number of subjects who have no Guardian Sensor inserted;

FAS^{#2}= Number of FAS^{#1} - Number of subjects who have no paired Guardian Sensor and YSI ^{TM*} measurement;

PPS= Number of FAS^{#2} - Number of subjects who have major protocol deviations (i.e. violate inclusion and exclusion criteria, etc.).

The listing of subjects who have no Guardian Sensor inserted or have major protocol deviations will be listed, including the center number, subject ID, randomly assigned FST, gender, age, type, details, FAS^{#1}, FAS^{#2} and PPS.

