6.5 Missing Values, Abnormal Value and Outliers

Data entry error or non-reasonable values will be cleaned before data analysis. Imputation of missing data will be only applied for sensitivity analysis. And strategies are as follows:

The missing paired YSI-SG is caused from the following cases but not limited to:

- Missing FST-YSI
- FST-YSI with deletion flag (from protocol deviations collected by CRF)
- · Existing FST-YSI value without paired SG point

Three imputation methods will be used for sensitivity analysis are as follows:

(1) Worst Case

- 1) 20/20% agreement rate: The missing paired YSI-SG will be filled with a 20/20% agreement of "No".
- 2) Zone of Clarke and Consensus Error Grid: The missing paired YSI-SG will be filled with a "Zone E".
 - 3) ARD (%): The missing paired YSI-SG will be filled with a maximum value from the study data.

(2) Best Case

- 1) 20/20% agreement rate: The missing paired YSI-SG will be filled with a 20/20% agreement of "Yes".
- 2) Zone of Clarke and Consensus Error Grid: The missing paired YSI-SG will be filled with a "Zone A".
 - 3) ARD (%): The missing paired YSI-SG will be filled with a minimum value from the study data.

(3) Randomly Pick from the Same Subject

- 1) The missing paired YSI-SG will be filled with a 20/20% agreement of random selection from the same subject.
- 2) The missing paired YSI-SG will be filled with a Zone of Clarke and Consensus Error Grid of random selection from the same subject.
- 3) The missing paired YSI-SG will be filled with an ARD (%) of random selection from the same subject.

For the dates of adverse events and medications collected during the trial, if the day or month or year is filled with "UK" or "NA", they will not be processed.

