7.1 Subject Disposition

The number of subjects enrolled in the study will be presented. The reasons for discontinuing prior to study completion will be summarized.

Version: V1.0

(1) Subjects Enrolled: Subjects who were enrolled in study.

- (2) Screening Failure: The subject did not meet eligibility criteria on visit 1 and did not enter visit 2: random assignment. (Does the subject meet all inclusion criteria, no exclusion criteria, and randomization conditions collected in CRF was "No").
- (3) Subjects Randomly Assigned FST: The subject entered visit 2: random assignment. (Does the subject meet all inclusion criteria, no exclusion criteria, and randomization conditions collected in CRF was "Yes").
- (4) Subjects entering FST: The subject inserted Guardian Sensor successfully and entered visit 4: FST with YSI^{TM*}. (This item is determined based on the subjects' YSI^{TM*} information).
- (5) Subjects completing the Study: Subjects completing Study: The subject completed the last visit. (This item is determined by the section study exit collected in CRF).
- (6) Subjects discontinuing from the study: The subject did not complete the last visit. (This item is determined by the section study exit collected in CRF).

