7.6 Primary Endpoints

Detailed analyses for four primary endpoints are as following:

- 1a) For the 20/20% agreement rate analysis, the analyses based on measurement level will be provided. Both the approximate normal distribution method and Clopper-Pearson method will be used to estimate primary endpoint based on measurement level. The 97.5% lower confidence limit of the agreement rate will be tested against corresponding threshold.
- 1b) Sensor values from primary sensor will be compared to YSI^{TM*} plasma glucose values during YSI^{TM*} FSTs. A mean rate in Zone A+B of Consensus Error Grid between Guardian Sensor (3) values and YSI^{TM*} plasma glucose values during YSI^{TM*} FST days.
- 1c) Sensor values from primary sensor will be compared to YSI^{TM*} plasma glucose values during YSI^{TM*} FSTs. A mean rate in Zone A+B of Clarke Error Grid between Guardian Sensor (3) values and

YSITM* plasma glucose values during YSITM* FST days.

1d) Sensor values from primary sensor will be compared to YSI^{TM*} plasma glucose values during YSI^{TM*} FSTs. A mean absolute relative difference (MARD) between Guardian Sensor (3) values and YSI^{TM*} plasma glucose values during YSI^{TM*} FST days.

At 1b) and 1c) evaluation criteria, both the approximate normal distribution method and Clopper-Pearson method will be used to analysis primary endpoint based on measurement level. The 97.5% lower confidence limit of the mean rate in Zone A+B of Consensus Error Grid, and the mean rate in Zone A+B of Clarke Error Grid will be tested against corresponding threshold, respectively.

At 1d) evaluation criteria, one sample T test will be used based on subject level and the 97.5% upper confidence limit of the MARD will be tested against corresponding threshold.

The study will be considered as a success only when the four evaluation criteria (1a), 1b), 1c), and 1d)) meet the pre-defined thresholds.

The analysis of primary endpoint will be performed on both the FAS^{#2} and PPS; and will be based on the available paired data only according to pairing scheme after considering YSI^{TM*} retention and sensor data retention principle.

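### The SAP Worst Case for 1a–1c runs on FAS#2, so a subject with YSI draws but no qualifying sensor–YSI pair is never scored, while a subject with a single pair has all other draws scored as failures

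*SAP*

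**What the plan says.** SAP 7.6 bases the primary analysis on observed pairs: it "will be based on the available paired data only according to pairing scheme", in FAS#2 and PPS. SAP 7.7 then gives the missing-data analyses, with the instruction "Sensitivity analyses will be performed on the FAS#2".

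SAP 6.3 defines FAS#2 as "a set of subjects who have at least one Guardian Sensor inserted and have at least one paired Guardian Sensor" and YSI measurement. SAP 6.4 removes from FAS#1 those who "have a Guardian Sensor inserted, but have no paired Guardian Sensor and YSI measurement". FAS#1, which needs only an inserted sensor, is assigned to baseline data.

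SAP 6.5 lists the causes of a missing pair, among them "Existing FST-YSI value without paired SG point". Worst Case fills a missing pair with a failure for 1a and with Zone E for 1b and 1c. Best Case fills it with a success and Zone A. For the third method, "The missing paired YSI-SG will be filled with a 20/20% agreement of random selection from the same subject" is the 1a rule, with matching rules for the error-grid zones.

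In SAP 7.1 a subject counts as entering FST if "The subject inserted Guardian Sensor successfully and entered visit 4: FST with" YSI. That definition does not require a pair.

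**The concern.** In the primary analysis the FAS#2 restriction is harmless. With observed pairs only, a subject without pairs contributes nothing whichever set is named. The restriction starts to matter in 7.7, because there the unpaired draws themselves are scored.

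The result is a Worst Case that does not worsen steadily as data are lost. Each lost pair adds a failure until the last one goes, and then the whole penalty disappears. The most complete form of a loss that 6.5 says to score is the one form left out. No other section brings these subjects into an analysis of 1a–1c.

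The situation is foreseeable. SAP 6.4 sets it out as its own category, and protocol 9.12.2 provides for a device download that cannot be read, which could leave YSI draws with no sensor values. A reader of the study report could take the Worst Case as the floor for everyone who had a sensor and an FST, which it would not be.

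**Working it through.** **Inputs.** From SAP 6.2: planning rates 0.65 against 0.60 (1a) and 0.95 against 0.90 (A+B, 1b and 1c), at least 20 points per subject, 60 subjects. From SAP 6.9: one-sided 0.025. From SAP 5.1: enrolment of up to 72. Assumed, because the documents give no figure: k no-pair subjects with 20 draws each, and no other missing pairs. Pairs are treated as independent, as the SAP plans.

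**The plan's own figure.** Power at n = 1,200 is Φ{[√n(pT − p0) − 1.96√(p0(1 − p0))] / √(pT(1 − pT))}.
- 1a: (1.7321 − 0.9602)/0.4770 = 1.618, power 94.7%.
- A+B: (1.7321 − 0.5880)/0.2179 = 5.25, power above 99.9%.

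Both agree with the stated power above 80%.

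**Lower limit.** L = p̂ − 1.96√(p̂(1 − p̂)/n). Clopper–Pearson, the SAP's other method, is in brackets.

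| Case | 1a: count, rate, L | A+B: count, rate, L |
|---|---|---|
| SAP Worst Case on FAS#2, any k | 780/1200, 65.0%, 62.3% (62.2%) | 1140/1200, 95.0%, 93.8% (93.6%) |
| 2 no-pair subjects scored on FAS#1 | 780/1240, 62.9%, 60.2% (60.2%) | 1140/1240, 91.9%, 90.4% (90.3%) |
| 3 no-pair subjects scored on FAS#1 | 780/1260, 61.9%, 59.2% (59.2%) | 1140/1260, 90.5%, 88.9% (88.7%) |
| 3 subjects with 1 correct pair and 19 unpaired draws, SAP rule | 783/1260, 62.1%, 59.5% (59.4%) | 1143/1260, 90.7%, 89.1% (89.0%) |

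The first and last rows show the asymmetry. Under the SAP's own rule, three subjects who keep one pair each turn both criteria to fail, and three who lose every pair change nothing.

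**Sensitivity to the assumptions.**
- With 28 draws per subject (7 h × 4 per hour), three no-pair subjects give 59.6% and 89.1%, and two give 60.6% and 90.7%. Three is still the first failure.
- If observed 1a agreement is 70%, seven no-pair subjects give 60.1% and eight give 59.2%.
- For A+B the first failure comes at four subjects if the observed rate is 97% (89.4%) and at five if it is 99% (89.9%).
- With enrolment capped at 72, at most 72 − 60 = 12 no-pair subjects are possible on this base. If 1a agreement is 80%, all 12 give 960/1440 = 66.7% and L = 64.2%, still a pass.

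**The case against.** Several points on the other side are fair.

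- **FAS#2 is defined by subject.** Its wording does not limit the pair to the primary sensor, and each subject wears two. A reader might infer that any sensor without a pair escapes scoring, and the text does not support that. If a recorder-sensor pair keeps the subject in FAS#2, the primary sensor's unpaired draws are scored, and the gap is limited to subjects in whom neither sensor gives a pair. The SAP does not say which reading applies.
- **Replacement narrows the gap.** Under protocol 9.6 and 9.7, if the primary sensor fails before the FST or within its first 5 hours, both sensors are replaced and the FST is rescheduled. Replacement is allowed once. A subject whose second set also fails may never reach an FST, and then there are no draws to score. An unreadable download is a data-handling loss and is not evidence of sensor error.
- **These analyses are supplementary.** SAP 7.7 names its population openly and does not promise a bound. The size of FAS#1 minus that of FAS#2 gives the no-pair count. This stands, but the count does not show the effect on 1a–1c.
- **The listing.** SAP 6.4 says "The listing of subjects who have no Guardian Sensor inserted or have major protocol deviations will be listed" and does not name no-pair subjects. The appendix with the listing shells is not among the documents, so one cannot conclude that they will go unlisted.
- **Low and High readings.** A reader might infer that out-of-range sensor readings are dropped without notice, because they are null in the SG column. Protocol 14.8.2 and SAP 6.6.2 declare the 40–400 mg/dL rule. What remains open is only whether 6.5 treats such readings as missing pairs.

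**Conclusion.** The concern holds in a limited form. For 1a–1c the Worst Case leaves out subjects who have YSI draws but no qualifying pair, although 6.5 counts such draws as missing pairs. It is therefore not a lower bound over subjects with a sensor and an FST. That follows from the text alone.

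The size is illustrative. It rests on an assumed number of no-pair subjects, 20 draws each, independent pairs and observed rates near the planning values. There, three such subjects separate a pass from a fail on both 1a and A+B, and two do not. With better observed agreement 1a is much less sensitive. A+B remains sensitive to four or five subjects even at 97% or 99%.

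A reader might infer that the trial's success decision is at risk. The documents do not support that: pass/fail rests on available pairs, this point leaves it unchanged, and the number of no-pair subjects may be zero.

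**What to change.** Keep the primary analysis and the pass/fail rule, and change the SAP as follows.

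1. In 7.7, run Worst Case and Best Case for 1a–1c on FAS#1, and count every YSI draw actually taken without a paired primary-sensor SG as a missing pair. Keep the random-selection method on FAS#2, since a subject with no pair has no donor value.
2. In 6.3, state that the qualifying pair for FAS#2 comes from the primary sensor.
3. Report no-pair subjects and unpaired draws by cause. Show subjects who had a sensor but no FST separately, since they have no draws to score.
4. Optionally, report counts of Low and High readings and state in 6.5 whether they are missing pairs.

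The cost is SAP wording, modest programming on data already collected, a few more tables, some judgement in assigning causes and possibly a less favourable sensitivity result. If no such subject occurs, moving to FAS#1 leaves the Worst and Best Case results as they were.

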7.8 Other Descriptive Endpoints

7.7.1 Clarke Error Grid Analysis (EGA) of Paired Sensor and YSI^{TM*} and Reference Values

1) Description

Clarke EGA separates paired observations into five zones of clinical significance. The presence and severity of possible treatment error based on interstitial glucose assay evaluated by the sensor defines the five zones. Zone A represents the absence of treatment error, where the evaluation method and the reference method are within 20% of one another or in which both methods indicate hypoglycemia. Zone B represents cases where the two methods disagree by more than 20%, but do not lead to treatment error. Zones C, D, and E represent increasingly large and potentially harmful discrepancies between the evaluation and the reference method. If the method under evaluation has a high percentage (greater than (>) 90%) of its pairs in Zones A and B, then it is considered clinically acceptable [Clarke et al, 1987].

2) Statistical analysis

Summary statistics (N, %) for each of the zones, as well as combined Zones A and B, will be calculated.

In order to evaluate differing levels of accuracy at various YSI™* defined glucose levels, the number and percentage of paired observations falling into Zones A, B, A+B, C, D, and E will be provide form YSI™* glucose ranges of ≤80 mg/dL, greater than (>) 80-120 mg/dL, greater than (>) 120-240 mg/dL, and greater than (>) 240 mg/dL.

All analysis performed using the Clarke Error Grid comparing the paired sensor and YSI^{TM*} reference glucose values will be duplicated using the Consensus Error Grid [Parkes et al, 2000].

7.7.2 Precision Analysis

Precision analysis will be performed for the two sensors worn by the same subject. This part of indicators will be summarized by descriptive statistics. The analysis method will be referred to section 7.2.

7.7.3 Other Accuracy Analyses

The ARD, the absolute relative differences between the sensor and YSI^{TM*} relative to the YSI^{TM*} reference will be calculated by FST days separately. Summary statistics will include its mean, standard deviation, min, median, and max.

The mean numerical bias, which is the difference between the sensor and YSI™* values, will be calculated by FST days. Summary statistics will include its mean, standard deviation, min, median, and max.

20% agreement rate will be summarized descriptively by FST days (Day 1, 3-5 and 7). A mean rate in Zone A+B of Clarke and Consensus Error Grid, a mean absolute relative difference (MARD) will also be summarized descriptively by FST days (Day 1, 3-5 and 7).

Above indicators will be summarized by descriptive statistics. The analysis method will be referred to section 7.2.

In addition, 20/20% agreement rate, a mean rate in Zone A+B of Clarke and Consensus Error Grid, a mean absolute relative difference (MARD) will be summarized descriptively by age subgroup (14-17 years old and 18-75 years old). The descriptive statistics and corresponding 95% confidence interval will be provided.

7.9 Safety Evaluation

For Safety analysis, no formal hypothesis testing will be performed. Descriptive analytics will be used to summarize safety events. Safety events which will be characterized include:

- 1) Skin assessment of GuardianTM Sensor (3) insertion sites
- 2) All adverse events (AEs) to include but not limited to:
 - a) Device Related AE
 - b) Procedure Related AE
 - c) Serious Adverse Event (SAE)
 - d) Serious Adverse Device Effects (SADE)
 - e) UADE
 - f) Severe Hypoglycemia
 - g) Diabetic Ketoacidosis (DKA)

7.10 Device Deficiencies

Descriptive summary will be used to characterize device deficiencies.

7.11 Subject Feedback

Descriptive summary will be used to characterize study questionnaire results. The questionnaire will use a Likert scale rating to assess their GuardianTM Sensor (3) experience.

7.12 Simulation Alert Calculation

The simulation alert calculation for the device 640G Pump and GS3 (Guardian™ Sensor 3) APP will be provided based on data collected in OC-RDC database and external device database.

- (1) Dataset preparation: The device dataset is prepared for alert calculation. The valid data should be after first valid ISIG. Any data before first valid ISIG should be excluded from analysis.
 - (2) Variables used for calculation: SBG, PSGV, ROC, and YSI^{TM*}/MBG where applicable.
- 1) SBG (Saturated Sensor Blood Glucose) is used for threshold alert analysis. Note: SBG is a saturated SG when SG <40, it sets to 40 or 400 when SG>400.
- 2) PSGV (Predictive Sensor Glucose Reading) is used for hypo predictive alert analysis of 640G Pump
- 3) ROC (Rate of Change of SG) is used for hyper predictive alert analysis of 640G Pump and for both hypo and hyper predictive alert analyses of GS3 APP. ROC-based predictive SG will be calculated with the formula: PSGV=SBG+ROC*30.
- (3) The CGM Setting: For hypo range, the CGM alert settings will be set as <= 50/60/70/80/90/100 mg/dL, respectively. For hyper range, the CGM alert settings will be set as >=300/250/220/180 mg/dL, respectively. Reference value YSI^{TM*} and SBG/PSGV threshold will keep changing as alert setting changes.
- (4) Calculation indicators and methods: Detection rate, missed detection rate, false alert rate and true alert rate will be calculated. For these four indicators, three types of simulation alert/event rates will be calculated. These three types are threshold, predictive and combined threshold and predictive, respectively. The detailed definition of above four indicators are below:
- 1) Detection Rate (% of Hypo/Hyper Events Correctly Detected): The device alarmed at the specified CGM settings within 30 minutes (or 15 minutes) before or after the reference blood glucose

value (YSI™* or MBG) goes at/below (for hypo) or at/above (for hyper) the specified CGM setting levels.

- 2) Missed Detection Rate (% of Hypo/Hyper Events Not Detected): The device did not alarm at the specified CGM settings within 30 minutes (or 15 minutes) before or after the reference blood glucose value (YSI^{TM*} or MBG) goes at/below (for hypo) or at/above (for hyper) the specified CGM setting levels.
- 3) False Alert (% False Alerts): There is no reference blood glucose value (YSI or MBG) goes below (for hypo) or above (for hyper) the specified CGM setting levels within 30 minutes (or 15 minutes) before or after the sensor alarmed at the specified alert settings.
- 4) True Alert (% of Alerts Verified by Hypo/Hyper Events): There is at least one reference blood glucose value (YSI or MBG) goes below (for hypo) or above (for hyper) the specified CGM setting levels within 30 minutes (or 15 minutes) before or after the sensor alarmed at the specified alert settings.

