9.9. YSI™* FST Instructions

9.9.1. Monitoring During the YSI™* FST

The frequency of blood draws for YSI™* FST sampling is dependent on the value of the previous sample, according to the following ranges:

- less than (<) 75 mg/dL (4.2 mmol/L); every 5 minutes (3-8 minutes)
- greater than (≥) 75 mg/L (4.2 mmol/L); every 15 minutes (7-23 minutes)

10768467DOC Version C

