6.6 General Considerations for Data Analysis

6.6.1 Data Collection

Analysis data source: The analysis of primary endpoints, other descriptive endpoints and simulation alert calculation will be based on both Oracle Remote Data Capture (RDC) database and external device dataset (collected sensor glucose data). The detailed specification of variables from external device data are as following:

- SG: Raw Sensor Glucose Reading
- PSGV: Predicted Sensor Glucose Reading
- SBG: Sensor Blood Glucose (values below 40 display as 40, values above 400 display as 400) elaborated below
- ROC: Rate of Change of SG
- ISIG: Interstitial Signal
- FORCALBG: Used in Calibration

The value "511" in the SG and PSGV column indicates "null". The SBG column will display saturated values of 40 if the reading was displayed as "Low" (i.e. if SG < 40 mg/dL) or 400 if the reading was "High" (i.e. if SG > 400 mg/dL) while the SG column will display 511. SG value of 40 is indicated when SG and SBG columns are equal to 40, and same for 400. SG column is used to generate the numerical calculation for sensor performance. SBG is used for alert analysis and sensor life analysis. PSGV and ROC columns are used for alert analysis.

In addition, primary endpoints, other descriptive endpoints, and functional sensor life time will be based on real-time data collected from primary sensor. Precision analysis will be based on data collected from both sensors.

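### ROC-based predictive alerts look 30 minutes ahead but are checked in ±30 or ±15 minute windows that end when the forecast falls due or earlier, so correct alerts can be scored false

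*SAP*

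**What the plan says.** SAP 7.12 simulates alerts retrospectively and reports four indicators (detection, missed detection, false alert, true alert) for three types: threshold, predictive and combined.

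- **Forecast.** "ROC-based predictive SG will be calculated with the formula: PSGV=SBG+ROC*30". This ROC-based value serves the 640G hyper alert and is also used "for both hypo and hyper predictive alert analyses of GS3 APP". The 640G hypo alert is different: "PSGV (Predictive Sensor Glucose Reading) is used for hypo predictive alert analysis of 640G Pump". SAP 6.6.1 defines the input only as "ROC: Rate of Change of SG", with no unit, and gives no horizon for the device PSGV.
- **True and false alert.** The period checked for each alert is "within 30 minutes (or 15 minutes) before or after the sensor alarmed at the specified alert settings". If at least one reference in that period is strictly past the setting, the alert is true. If none is, it is false; the SAP words the second case as "There is no reference blood glucose value (YSI or MBG) goes below (for hypo) or above (for hyper) the specified CGM setting levels".
- **Detection.** Here the window is centred on the reference event, which must reach or pass the setting: "The device alarmed at the specified CGM settings within 30 minutes (or 15 minutes) before or after the reference blood glucose". Missed detection is the complement.
- **Reference sampling.** Protocol 9.9.1 draws YSI every 5 minutes (3-8) when the previous value is below 75 mg/dL; otherwise draws come "every 15 minutes (7-23 minutes" allowed).

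No separate window is given for predictive alerts. The SAP text does not say whether one alert per excursion or every alarming reading is counted.

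**The concern.** A threshold alert says that glucose is past the setting now, so a symmetric window around the alert suits it. A predictive alert says that glucose will be past the setting in 30 minutes. A window that closes at 15 minutes ends halfway to the event. A window that closes at 30 minutes ends about when the event is due, and the first YSI sample past the setting can come up to one draw interval later. References exist inside the window, but the forecast has not yet come due, so a correct alert is recorded as false.

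Alert performance across the hypo- and hyperglycemia ranges is the first descriptive endpoint in protocol 5.2.2. Alerts are switched off during the study (protocol 7.1.1), so these definitions alone produce the reported rates. Under first-alert scoring they also reward lateness: a lagging sensor scores better than one that alerts on time.

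A smaller inconsistency sits in the same item. Detection and missed detection count a reference at or past the setting. True and false alert require it to be strictly past. A reference equal to the setting can be a detected event while the alert that found it is false.

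**Working it through.** The plan states no rate for this analysis, so there is no figure to reproduce.

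**Inputs**
- Horizon: 30 (SAP 7.12), read as minutes. This is an assumption, because ROC has no stated unit.
- Half-window w: 30 or 15 minutes (SAP 7.12).
- YSI interval d: 15 minutes at 75 mg/dL or above (7-23 allowed), 5 minutes below (protocol 9.9.1).
- Sensor reading interval: 5 minutes. This is an assumption, consistent with the [0, 5) pairing in SAP 6.6.2.
- Straight-line glucose path, exact ROC, and sensor lag L of 0, 5 or 10 minutes: assumptions.

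**Step 1: first alert of an excursion.** The first alarming reading precedes the true crossing by 30 − U − L minutes, with U uniform on (0, 5). The first reference past the setting follows the crossing by V, uniform on (0, d). The alert is verified when 30 − U − L + V ≤ w.

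- w = 15: this needs V ≤ U + L − 15. Since U ≤ 5 and L ≤ 10, the right side is never above zero. Verified: **0%** for every lag tried.
- w = 30: this needs V ≤ U + L.

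| Draws | Lag | Verified |
|---|---|---|
| 15 min (settings ≥ 80 mg/dL) | 0 | 2.5/15 = 16.7% |
| 15 min | 5 min | 7.5/15 = 50% |
| 15 min | 10 min | 12.5/15 = 83.3% (about 84% simulated) |
| 5 min (setting 50 mg/dL) | 0 | 2.5/5 = 50% |

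At settings of 60-70 mg/dL the draws change from 15 to 5 minutes on the way down. Simulation without lag gives about 22-50% there, depending on the rate of fall.

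**Step 2: every alarming reading, from 30 minutes before to 30 minutes after the crossing, no lag.** Readings from V − w onward are verified, so the mean share is (30 + w − d/2)/60.

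- w = 15: 37.5/60 = 62.5% (d = 15) to 42.5/60 = 70.8% (d = 5). Simulated: about 63-72%.
- w = 30: 52.5/60 = 87.5% to 57.5/60 = 95.8%. Simulated: about 87-96%.

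**Step 3: how long the window must be.** The first reference past the setting comes at most 30 + max(V) minutes after the first alert: 45 minutes with exact 15-minute draws, 53 minutes with the permitted 23.

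A 45-minute limit verifies an alert when V ≤ 15 + U (no lag). If intervals are uniform over 7-23 minutes (an assumption, mean 15), V has density (23 − x)/(16·15) above 7 minutes, so P(V > 15 + u) = (8 − u)²/480. Averaged over u from 0 to 5 this is (512 − 27)/(15·480) = 485/7200 = 6.7%, leaving **93.3%** verified. If every interval is 23 minutes, 17.5/23 = **76.1%**. A 53-minute limit verifies 100%.

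**The case against.** The strongest reply is that a reader might infer that predictive alerts are mostly scored false, and the documents do not support that in general.

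- **Counting rule.** The SAP text does not fix it, and the table shells were not available. If every alarming reading is counted through 30 minutes after the crossing, most are true in both windows (step 2). Stopping at the crossing gives (w − d/2)/30: 75-92% at ±30, but only 25-42% at ±15.
- **Lag.** The 17% figure needs a sensor with no lag. With a 10-minute lag most first alerts are verified at ±30, and a crossing exactly 30 minutes later does lie inside that window.
- **Scope.** The 30-minute formula does not drive the 640G hypo alert. Combined alerts include threshold alerts, for which the present windows are reasonable, and the effect on their rates was not calculated. Neither set of rates can be called wrong on this evidence.
- **Weight.** The endpoint is descriptive, carries no hypothesis, and is already reported at two window widths.

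All of this narrows the point, and none of it removes it. Two window widths do not help when neither extends beyond the horizon. The ±15 result for first alerts is zero at every lag tried, and under per-reading counting some correct alerts are still recorded as false. The open counting rule adds to the problem: without lag, the same perfect sensor scores 0% or about 70% at ±15, depending on a choice that the SAP text does not make.

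**Conclusion.** The point holds for the ROC-based predictive alerts: GS3 app hypo and hyper, and 640G hyper. With ROC per minute, 5-minute readings and an error-free sensor, ±15 minutes cannot verify a correctly timed first alert. For first alerts ±30 minutes is marginal: about 17% without lag where YSI is drawn every 15 minutes, rising to about 50% and 84% with 5- and 10-minute lag. Per-reading counting is far milder but still leaves about 28-37% of correct readings unverified at ±15, and about 4-13% at ±30 (the complements of 63-72% and 87-96%).

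Two wider readings are not supported: that most predictive alerts will be scored false whatever the counting rule and lag, and that all predictive and combined rates are affected to this degree. The figures use YSI references only; meter values were not modelled. The four primary criteria and the study's pass/fail result are untouched. The mismatch between the at-or-past and strictly-past definitions needs no assumption.

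**What to change.** In SAP 7.12 (4):

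1. For ROC-based predictive alerts, add a true/false alert window from 30 minutes before to 53 minutes after the alert (30-minute horizon plus the 23-minute maximum YSI interval). Forty-five minutes covers only the nominal 15-minute draw.
2. Apply the matching look-back to detection and missed detection: an alert counts if it fell from 53 minutes before to 30 minutes after the reference event.
3. Make this the main predictive result, and keep the ±30 and ±15 tables for comparability.
4. State whether one alert per excursion or every alarming reading is counted, the unit of ROC, and the horizon of the device PSGV used for the 640G hypo alert.
5. In items 3) and 4), count references at or past the setting, as items 1) and 2) do.

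The cost is a few lines of SAP text, one program parameter and one extra set of tables, with no new data. The small downside is that a longer window verifies a few more alerts by chance; keeping the present tables lets the reader see how much the rates move.
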